7.4 Outcomes

The goal of this study is to supply patients and families with the information about the risks and benefits of PFDD and PFD that *they feel* are most important in making informed clinical decisions. As such, the primary outcome of interest is reduction in harm to patients, measured as surgical complications and/or requirement for reoperation for complication management ≤ 12 (+/- 2 months) months after initial PFDD or PFD. Complications and reoperation are associated with additional pain as well as emotional and psychological stress, longer hospital stays, and lost time from school/work. Secondary outcomes focus on efficacy outcomes and will include: 1) comparison of pre-operative symptoms and neurological deficits at ≤ 6 weeks, 3-6 months, and 12 (+/- 2 months) months after surgery and syrinx size and spinal alignment (coronal and sagittal Cobb angles) at 12 (+/- 2 months) months after surgery. This outcome will be evaluated using the CHIP and the HUI-3 QOL instruments where analyses based on CHIP will be used as the primary results for aim 3 in case CHIP and HUI-3 results do not agree.

Because this is a surgical trial, an Adjudication Committee, consisting of two pediatric neurosurgeons and one pediatric neuroradiologist independent of the design and conduct of the trial, will adjudicate the primary outcome measure. The committee will review the primary endpoint based on a blinded review of clinical notes, data forms and imaging studies. Decisions by the adjudication committee will determine final outcomes. Consensus definitions of CSF-related complications following neurosurgery have been developed [34]. These definitions have been reviewed and approved by the neurosurgeons participating in the study and will be used in this trial. Likewise, the extent of syrinx resolution following surgery will be determined by centralized review of blinded imaging studies. By contrast, treatment failure (i.e. need for revision PFDD or PFD) will be determined individually by the treating surgeon in consultation with the patient/family, since such decisions are inherently subjective and based both on the surgeon's level of concern and the patient's discomfort and relative acceptance to the inherent risks of surgery (either PFD or PFDD).

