7.5 Data Analyses

A Priori Plans for Data Analysis

Descriptive Statistics

Using CONSORT guidelines for cluster-randomized trials,53 We will present descriptive statistics, for continuous variables the mean (+/-standard deviation) or median (minimum, maximum) values and for categorical variables the frequencies and proportion for each cluster. These presentations will be carried out at baseline and at 12-month follow-up. We will provide reasons for dropouts.

Final Comparative Analysis PCORI CER-1503-29700 Based on Protocol Version 6 March, 2021 *Planned sensitivity analyses to determine the impact of key assumptions.* Due to the fact that each patient in a given center will be assigned to the same procedure, it is possible to observe unequal overall sample sizes for each procedure. The initial analysis plan is to give equal weights to all clusters. If there is imbalance in the prognostic factors, we will use weighted analyses where the cluster-level summary score is weighted inversely proportional to the reciprocal of its estimated variance.

Initial analysis will be conducted using per Treatment group assignment prior to adjudication, as it aligns more to in-practice clinical procedures. Sensitivity analyses will be conducted based upon Intent-to-Treat (ITT) (as randomized), and per Protocol (actual treatment) grouping definitions, both pre and post adjudication. Patients with a second Chiari surgery will be analyzed in two different ways in sensitivity analysis, one including vs one excluding second surgeries. and will be.

Comparison methods

Specific Aim 1: Hypothesis: PFD will be associated with fewer surgical complications and less potential harm to patients than PFDD.

Anticipated Outcome: Cerebrospinal fluid (CSF)-related complications ≤ 6 months (e.g. CSF leak, pseudomeningocele, aseptic meningitis, infection, hydrocephalus), and the requirement for additional surgery for wound revision or CSF diversion will be lower after PFD compared with PFDD.

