The primary outcome is a binomial outcome measured as a surgical complication and/or requirement for reoperation for complication management ≤ 12 (+/- 2 months) months after initial PFDD or PFD. To account for within cluster correlation, possibly variable cluster size and the relatively small number of clusters in this cluster randomized trial, generalized estimating equations (GEE) with small-sample correction or random effect logistic regression will be used for the primary analysis of this cluster randomized trial [35, 36].

Specifically, a GEE model with a logit link function and adjustment for baseline covariates can be expressed as follows:

$logit(\pi_{ij}) = \mu + \delta T_i + x_{ij}\beta$

where $T_i = I$ if group *i* is assigned PFD and 0 otherwise. Accordingly, δ is the intervention effect. Let x_{ij} is the p-dimensional vector of group-level of individual level covariates from individual *j* (*j* = 1, ..., n_i) nested in center *i* (*i* = 1, ..., # of active centers here); and β is the vector of covariate effects. Also let the outcomes (CSF-related complication ≤ 6 months, yes/no) are independently distributed as $y_{ij} \sim \text{Bernoulli}(\pi_{ij})$. Further let, μ be the log-odds of positive outcome ($y_{ij} = 1$) for PFDD subjects with reference values for covariates ($x_{ij} = 0$) and average random effect ($\gamma_i = 0$). The exchangeable correlation structure will be used for the within-group homogeneity for the correlation structure of the outcomes. Note that, this correlation parameter corresponds to the intraclass correlation coefficient (ICC).

Specific Aim 2:

Hypothesis: Clinical improvement and syrinx regression provided by PFD will be non-inferior compared to those provided by PFDD.

Anticipated Outcome: Clinical symptoms, neurological function, and syrinx regression ≤ 12 months (± 2 months) provided by PFD will be non-inferior compared to those provided by PFDD. The non-inferiority margin is defined as the difference between the outcome rates by treatment. For the clinical improvement outcome, a non-inferiority margin of 0.17 units will be used. A non-inferiority margin of 0.135 units will be used for the syrinx regression outcome.

Clinical symptoms, neurological function, and syrinx regression are defined as rates of change from baseline to 12 months. The 1-sided confidence interval for the difference in rates between the PFD and PFDD groups will be calculated and compared to the corresponding non-inferiority margins.

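### On its plainest reading, SAP 7.5 bases the lead Aim 1 result on unadjudicated outcomes and an undefined grouping, while SAP 7.4 and Protocol 9.4 give the blinded committee the final say

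*SAP*

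**What the plan says.** **Adjudication.** SAP 7.4 (Outcomes) sets up an independent Adjudication Committee for the primary outcome: "The committee will review the primary endpoint based on a blinded review of clinical notes, data forms and imaging studies". It continues: "Decisions by the adjudication committee will determine final outcomes". Protocol 9.4 has the same rule.

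**Lead analysis.** SAP 7.5, under Final Comparative Analysis, states: "Initial analysis will be conducted using per Treatment group assignment prior to adjudication, as it aligns more to in-practice clinical procedures". The next sentence reads: "Sensitivity analyses will be conducted based upon Intent-to-Treat (ITT) (as randomized), and per Protocol (actual treatment) grouping definitions, both pre and post adjudication". Both follow an italic lead-in, "Planned sensitivity analyses to determine the impact of key assumptions". The paragraph just before them says: "The initial analysis plan is to give equal weights to all clusters". The matching text in Protocol 9.5 has the equal-weights sentence but nothing about analysing before adjudication.

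**Aim 1 model.** Under Specific Aim 1, SAP 7.5 says that GEE with a small-sample correction, or random-effect logistic regression, "will be used for the primary analysis of this cluster randomized trial". The treatment term equals 1 if the centre "is assigned PFD and 0 otherwise". That text does not say whether the outcome is the adjudicated one.

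**Grouping label.** *Per Treatment* appears twice in the SAP, in Final Comparative Analysis and in Secondary Analysis (both in 7.5). It is defined in neither place.

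**The concern.** Two separate things are unsettled in the analysis that decides the trial's main question.

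The first is the outcome version. A blinded committee whose decisions are final should supply the data for the headline result. SAP 7.5 appears to start from the data before the committee has acted and to give every adjudicated version sensitivity status. Protocol 5.1 says each centre knows its arm before it enrols anyone, so unadjudicated outcomes come from unblinded sites. Some components need judgement: under SAP 7.5.1, chemical meningitis is diagnosed clinically and no lumbar puncture is required. Blinded review exists to protect this kind of endpoint.

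The second is the grouping. If a planned procedure is changed in theatre, an analyst who reads *per Treatment* as assigned and one who reads it as received would build different lead datasets, and both could claim to have followed the SAP.

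**Working it through.** This is mainly a matter of setting the texts side by side. The arithmetic only illustrates scale.

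**Step 1. Which outcome version leads?**

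| Source | What it fixes |
|---|---|
| SAP 7.4, Protocol 9.4 | Blinded committee adjudicates the primary outcome; its decisions are final |
| SAP 7.5, Final Comparative Analysis | Initial analysis precedes adjudication; post-adjudication versions are sensitivity analyses |
| SAP 7.5, Specific Aim 1 | Primary model and assignment coding; silent on outcome version |
| Protocol 9.5, Final Comparative Analysis | Silent |

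Only the second row ties an outcome version to an analysis, and it points away from the first row. The sentence covers all three aims, but the committee adjudicates the primary outcome, so the conflict falls on Aim 1.

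**Step 2. What could *per Treatment* mean?**

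- *As assigned.* This fits the Aim 1 model but is the same as the intention-to-treat analysis listed as sensitivity.
- *As received.* This is the same as the actual-treatment analysis listed as sensitivity. It does not fit a treatment term coded once per centre by assignment.

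The stated reason, closeness to clinical practice, does not choose between them. The choice matters only if an operation is changed, which SAP 6 calls highly unlikely.

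**Step 3. The plan's own sample-size figure (background).** SAP 7.2 gives 136 patients, unclustered, for 17.8% against 2.7% with 84% power and two-sided 0.05. With pooled variance:

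- mean rate = (0.178 + 0.027)/2 = 0.1025
- n per arm = [1.960 × √(2 × 0.1025 × 0.8975) + 0.994 × √(0.178 × 0.822 + 0.027 × 0.973)]² / 0.151² ≈ 68.95, so 69 per arm and 138 in total
- power at 68 per arm = 83.5%, against 84% stated

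The figure reproduces closely. It assumes no crossover and no outcome misclassification, so naming the adjudicated, as-randomised analysis as primary leaves the planned 148 unchanged.

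**Step 4. How many reclassified events would matter?** The inputs are 74 per arm and the planned rates: 0.027 × 74 = 2.0 and 0.178 × 74 = 13.2, taken as 2 and 13 events. The test is two-sided Fisher exact and ignores clustering, so it is not the planned GEE. Every reclassification is assumed.

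| Assumed change on adjudication | PFD | PFDD | p |
|---|---|---|---|
| None | 2/74 | 13/74 | 0.0048 |
| Three PFDD events overturned | 2/74 | 10/74 | 0.0312 |
| Four PFDD events overturned | 2/74 | 9/74 | 0.0557 |
| One PFD and three PFDD overturned | 1/74 | 10/74 | 0.0090 |
| One event added to each arm | 3/74 | 14/74 | 0.0083 |
| One PFD event overturned | 1/74 | 13/74 | 0.0011 |
| Two PFDD events added | 2/74 | 15/74 | 0.0013 |

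Reclassification can weaken or strengthen the result. At planned rates, overturning PFDD events alone crosses 0.05 only at the fourth of 13.

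**The case against.** **The sentence says initial, not primary.** The SAP keeps the word primary for the model under Specific Aim 1, and the sentence follows a sensitivity-analysis lead-in. One could read it as a first run on recorded data, with the committee's outcomes final. This stands as a reason for caution. Against it, the following sentence separately introduces sensitivity analyses and puts every adjudicated version there, the preceding paragraph uses initial for its default plan, and nothing else names an adjudicated lead analysis.

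**Adjudication may refer to grouping.** The grammar allows it in both sentences, and the stated reason concerns procedures rather than how complications are ascertained. But the documents describe adjudication only of the primary outcome and of uncertain eligibility (Protocol 6.2.1), never of treatment group. On this reading there would be no conflict with SAP 7.4, but the SAP would rely on a process it does not describe.

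**The consequence may be small.** Consensus definitions apply. Hydrocephalus requires an intervention, and the reoperation items are procedures. Adjudicated results would be reported, so a divergence would be visible. All of this stands, and it limits the likely effect without settling which result is primary.

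**Protocol 9.5 is only silent.** Agreed. Its silence is not a contradiction; the conflict is with SAP 7.4 and Protocol 9.4.

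A reader might infer that the lead grouping has no adjudicated counterpart at all. The documents do not support that. On either meaning in Step 2, *per Treatment* coincides with a grouping that is planned both before and after adjudication.

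**Conclusion.** The concern holds in this form: SAP 7.5 does not say clearly which outcome version and grouping are primary for Aim 1, and on its plainest reading it contradicts SAP 7.4 and Protocol 9.4. Confidence is moderate to high for the conflict, given the two alternative readings, and high that *per Treatment* is undefined.

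The numerical effect cannot be stated. The Step 4 figures rest on assumed reclassifications, planned event rates and a test that ignores clustering. They show a planned-size result that survives three overturned PFDD events but not four. The case for correction rests on the contradiction over the data behind the primary endpoint, not on those figures. The grouping half is the smaller part, since it needs a change of procedure during surgery to have any effect.

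Two stronger inferences should be resisted. One is that site-recorded outcomes would favour a particular arm: the documents show no direction of bias. The other is that the choice was made after seeing data, because the SAP is dated July 2021 and enrolment was proposed to end on December 31, 2018. The dates alone do not show that.

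**What to change.** In SAP 7.5:

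1. State that the Aim 1 primary analysis is by randomised centre (intention-to-treat, as the model is already coded) and uses committee-adjudicated outcomes, as SAP 7.4 and Protocol 9.4 require.
2. Keep the pre-adjudication and actual-treatment versions as sensitivity analyses.
3. Define *per Treatment* or delete it, in both Final Comparative Analysis and Secondary Analysis.

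The cost is a few sentences. The adjudicated intention-to-treat analysis is already planned, so no new data are needed. The decision rules for Aims 2 and 3 are not affected.

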For the purpose of sample size estimation, data from in the Park-Reeves Syringomyelia Research Consortium (PRSRC) were analyzed (ambispective enrollment, n=589 subjects with complete data); specifically, surgical complications ≤ 12 months were used to calculate the sample size. In this dataset, surgical complications were noted in 17.8% of PFDD cases and 2.7% of PFD cases. This is consistent with reported values from a recent meta-analysis, where the rates for CSF-related complications for PFDD and PFD were 18.5% and 1.8%, respectively [27], as well data reported in case series [17, 25] and a systematic review [42]. We expect to observe a similar difference in PFDD versus PFD cases in the proposed study. Because of the clustered randomized nature of the trial, the intraclass correlation coefficient (ICC) should be taken into account. The ICC is defined as the proportion of the between cluster (PRSRC center) variation to the total variation. Since the cluster sizes are small (6 per PRSRC center), and we have a large number of centers available for enrollment (47 total), the effect of ICC on sample size will be small. Thus, using the PRSRC values of 17.8% for PFDD and 2.7% for PFD, and assuming equal number of subjects per group and twosided type I error rate of 0.05, to reach 90% power, 36 centers averaging 6 subjects per center will be required for the trial assuming the ICC is 0.05. To account for 2% dropout rate, we originally planned to recruit 40 centers with a cluster size averaging 6 subjects with overall sample size of enrolled patients of 240 patients, approximately 120 patients per procedure over the two years of enrollment.

Aim 1: Sample Size Recalculation (November 29, 2017)

The original sample size calculation was performed based on surgical complication rates (≤ 12 months) from Park-Reeves Syringomyelia Research Consortium (PRSRC) estimates (17.8% in PFDD and 2.7% in PFD cases). We originally did not have an estimate for the ICC. Based on the literature, we assumed ICC of 0.05 in our calculations [43]. The overall sample size of enrolled patients would be 240 patients, approximately 120 patients per procedure over the two years of enrollment.

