In preparation for our PFD trial annual meeting on November 29, 2017, we performed a sample size re-calculation, using the ICC observed from the 47 patients enrolled in the study and for which complete data was available as of November 28, 2017. It should be noted that the data was only used to calculate the ICC; no interim analyses were performed. The ICC based on the first enrolled 47 patients was 0.000059, much smaller than what was assumed (0.05) for the original sample size calculation. However, we expect this ICC estimate to change with more enrollments.

Enrollment in the trial has increased over time and continues to do so (for example, 10 patients were enrolled in both November and December, 2017 and the total trial enrollment is now 83). However, when calculated at the time of the annual meeting at the end of November 2017, the average accrual rate, calculated over the entire 19-month period of the study, was 6 patients per month. Thus, using the conservative projection of 6 patients per month over the course of an enrollment extension ending 12/1/2018, we expect the total number of subjects to be at least 145 (73 + 12 x 6). (73 was the total enrollment when these calculations were made at the end of November; however, as noted above, 10 patients were recruited in December.)

Based on the enrolled 47 patients in the database with complete data as of 11/28/17, the average cluster size is 2.9. If we assume each center enrolls 3 more patients over the enrollment extension, the average cluster size increases to 5.9. With the current ICC estimate of 0.01 and using the original estimates for the complication rates (17.8% in PFDD and 2.7% in PFD), with the projected sample size of 145, we can still reach 84% power by enrolling patients from 24 centers with an average cluster size of 6 (144 subjects total). The same power level can also be achieved by enrolling patients from 30 centers with an average cluster size of 5. To account for a potential 2% loss to follow up rate, we planned to recruit 148 subjects total (74 per group) over the entire trial enrollment period.

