It should be noted that it is assumed that the average cluster size is 6 in all centers for these calculations. The design effect (DE) concept is used in cluster randomized trials to inflate the sample size of the study, compared to the traditional randomized trials [44]. When cluster size is fixed, $DE = 1 + [(m - 1) \times ICC]$; where m is the average cluster size and ICC is the intraclass correlation coefficient. In other words, the sample size of the study can be calculated by traditional methods, and should be multiplied by the DE. Under the assumption that m = 6 and ICC = 0.01, DE becomes 1.05. To compare 17.8% vs 2.7% surgical complication rates for a (*not clustered*) randomized trial, with 84% power, and 0.05 type I error rate, we would need to enroll 136 patients total. This is also listed in the sample size calculator above under the "unadjusted box". For a DE value of 1.05, this sample size should be multiplied by 1.05 to find the sample size of a cluster randomized trial to reach same power. Therefore, the sample size of the clustered randomized trial would be 136 x 1.05 = 142.8 ~143.

The variable cluster size is common in cluster randomized trials. Eldridge et al considered the effect of variable cluster size on the sample size calculation for cluster randomized trials [45]. They showed that the DE value can be calculated for variable class sizes. DE' = $1 + {(cv^2+1) m - 1} x$ ICC; where cv is the coefficient of variation of cluster sizes (standard deviation of cluster sizes divided by the mean cluster size). The cv is 1.08 for our study. If we use the current average cluster size of m = 2.9, DE' becomes 1.06. In other words, the sample size of the study should be inflated to 136 x 1.06 = 144.16~145 to reach 84% power. This assures us that our planned sample size of 145 patients will allow us to reach 84% power even if our cluster sizes will not be fixed at 6.

It should be noted that, as of March 6th 2018, only 1 of 100 enrolled patients was lost to followup. However, to account for a potential 2% loss to follow up on the 145 subjects needed (72 per group), we will recruit 148 subjects total (74 per group) over the entire trial enrollment period, which is proposed to be extended to December 31, 2018.

Aim 2: Non-Inferiority Margins and Power

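### The 84% power stated for Aim 1 comes from a two-proportion calculation and does not describe the small-sample-corrected logit GEE planned as the primary analysis; with the usual Wald test, power is roughly 60–80%

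*SAP*

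**What the plan says.** **Sizing.** The November 2017 recalculation (SAP 7.2.1; Protocol 9.5, Aim 1) keeps complication rates of 17.8% for PFDD and 2.7% for PFD. For an unclustered trial it says that "with 84% power, and 0.05 type I error rate, we would need to enroll 136 patients total". It then applies a design effect: "Under the assumption that m = 6 and ICC = 0.01, DE becomes 1.05". The result is about 143–145 patients, and the SAP concludes that "we can still reach 84% power by enrolling patients from 24 centers with an average cluster size of 6". It adds: "The same power level can also be achieved by enrolling patients from 30 centers with an average cluster size of 5". The test behind the 136 is not named. The two-sided 5% level is stated with the original calculation: "assuming equal number of subjects per group and twosided type I error rate of 0.05, to reach 90% power".

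**Analysis.** SAP 7.5 (Comparison methods, Specific Aim 1) allows a GEE with small-sample correction or a random-effect logistic regression, and writes out only the first: "Specifically, a GEE model with a logit link function and adjustment for baseline covariates can be expressed as follows". The coefficient δ of the PFD indicator is called the intervention effect, so it is a log-odds ratio. The working correlation is exchangeable.

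**Not stated in either document.** The test statistic, the small-sample correction, the reference distribution and its degrees of freedom, the Aim 1 covariates, what to do if the PFD arm has no events, and the power of the logit analysis.

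**The concern.** The power figure and the primary analysis belong to different tests. At 2.7%, 72 PFD patients yield about 1.9 expected events. With so few, the standard error of a log-odds ratio is set almost entirely by the PFD arm, and an estimate may not exist at all. A z test of two proportions suffers far less from this. If the primary analysis is a Wald test of δ, the trial has a lower chance of detecting its own planning difference than the documents state. Because the choices that decide the power are open, they could also be settled after the data are seen.

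**Working it through.** **Inputs.** 17.8% and 2.7%; 1:1; two-sided 0.05; 24 × 6 = 144 or 30 × 5 = 150; ICC 0.01; design effect 1.05; 72 evaluable per group; cv of centre size 1.08 (all SAP 7.2.1).

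**1. The plan's own figure.** Mean rate = (0.178 + 0.027)/2 = 0.1025; difference = 0.151. At n = 68 per arm:
- null SE = √(2 × 0.1025 × 0.8975/68) = 0.0520
- alternative SE = √((0.1463 + 0.0263)/68) = 0.0504
- pooled z: (0.151 − 1.96 × 0.0520)/0.0504 = 0.97, power 83.5%
- unpooled z: 0.151/0.0504 − 1.96 = 1.04, power 85.0%

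At 72/1.05 = 68.6 per arm the pooled figure is 83.8%. The printed 84% is therefore a two-proportion z calculation; which variance formula was used makes little difference.

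**2. Wald test of δ, analytic.**
- log-odds ratio = ln(0.178/0.822) − ln(0.027/0.973) = −1.530 + 3.585 = 2.055 in absolute size
- SE at 68.6 per arm = √[1/(68.6 × 0.1463) + 1/(68.6 × 0.0263)] = √(0.100 + 0.555) = 0.809
- the PFD arm supplies 0.555/0.655 = 85% of the variance
- 2.055/0.809 − 1.96 = 0.58, power 71.9% (normal); 68.0% with t on 22 df and 68.8% with t on 28 df

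**3. Trials with no PFD event.** For independent patients the chance is 0.973^72 = 13.9%; in clustered simulation it is about 13–15%. The logit estimate is then infinite. Software returned values near −25 with a standard error near 0.5 and rejected in every such trial, which is an artefact of separation.

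**4. Simulation.** 24 centres of 6, beta-binomial with ICC 0.01, no covariates, t with 22 df, and one of two standard small-sample corrections of the sandwich variance. Correction A is the more conservative (the second of the two named under the fix); correction B is the milder (the first named there). Power:

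| Zero-event trials | Logit Wald, A / B | Risk difference, A / B |
|---|---|---|
| count as failures | 60% / 64% | 67% / 70% |
| left out | 71% / 76% | 79% / 83% |
| count as successes | 75% / 79% | 82% / 85% |

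Separate simulations agreed within about one point. Within any row the logit link costs 6–8 points.

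**5. Other settings, logit Wald.**
- Zero-event trials as failures: a normal reference gives 66–69% at 24 × 6; 30 × 5 gives 67–70% with t and 70–73% with a normal reference.
- The most favourable combination (30 × 5, correction B, normal reference, zero-event trials counted when an exact test of the two proportions is significant) gives 85.5%.
- Unequal centres, zero-event trials as failures: about 45–56% at a cv near 1.08, and 48–66% in a second simulation at a cv near 0.9.

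**6. Same logit GEE, score test of δ = 0.** A robust score test with the (K − 1)/K adjustment, K being the number of centres, gives 81% (t) and 85% (normal) at 24 × 6, and 84% and 87% at 30 × 5. The form of the adjustment moves these by a few points. The test is fitted under the null, with both arms pooled, so it stays defined when the PFD arm has no events.

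**The case against.** The best reply is that the SAP never says Wald. It specifies a model and a link, and step 6 shows that a score test of δ in that model roughly attains the stated power. SAP 7.5 also permits random-effect logistic regression; ignoring clustering, a likelihood-ratio test has about 89% power at 68 per arm, although such tests can be liberal at very low rates. All of this stands. It means the shortfall belongs to the usual way of testing δ and not to the model as written.

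A reader might infer that the primary analysis simply has 61–65% power, that it would miss the assumed effect in more than one trial in three, and that the log-odds scale is the whole cause. The documents do not support that. The figure needs a Wald test, a t reference, the 24 × 6 design and every zero-event trial counted as a failure, and the SAP fixes neither the test, the reference nor the zero-event rule. Comparing it with the 82–85% of a risk-difference analysis is also uneven, because that analysis declares nearly all the zero-event trials significant, its PFD-arm variance then being zero.

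It can also be said that enrolment was proposed to end in December 2018 and the SAP is dated July 2021, so a power figure no longer changes the sample size. That is true, and restating power affects neither the estimate nor the type I error. The choice of primary test still affects the chance of detecting the difference, and it should not be left to be made on the data.

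**Conclusion.** The point holds in a limited form. The 84% does not describe the primary analysis of SAP 7.5. With a corrected-sandwich Wald test of δ, power at the plan's own rates is about 61–65%, 71–76% or 75–80% at 24 × 6 according to how zero-event trials are treated. It is a few points higher at 30 × 5 or with a normal reference, and lower with unequal centres; analytic Wald power is 68–72%. The stated 84% is reached only at the favourable edge of these choices. The loss comes from a Wald test on the log-odds scale combined with about two expected PFD events; the link alone accounts for about 6–8 points.

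These figures assume beta-binomial clustering at ICC 0.01, equal centres unless stated, and no covariates, since the SAP names none for the Aim 1 model. Random-effect logistic regression was not simulated with clustering.

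**What to change.** In SAP 7.5, Aim 1, settle on one primary test that comes close to the planned power and stays usable with 0 or 1 PFD events. Either of these would serve:
- the small-sample-adjusted robust score test of δ in the logit GEE, with its adjustment and reference distribution stated; or
- the PFD − PFDD risk difference from a GEE clustered by centre, with a named correction (for example Kauermann-Carroll or Mancl-DeRouen) and t with centres − 2 df. Simulated type I error was about 4–5%.

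Choosing between them is a matter of preference; an identity link is not required. In either case, add a rule for reporting the effect when the PFD arm has no events, report the other effect measure as supportive, and remove the open choice between GEE and random-effect logistic regression.

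If the Wald test of the log-odds ratio is kept, replace 84% in SAP 7.2.1 and Protocol 9.5 with the simulated power of that exact analysis, about 60–80% depending on the correction, reference distribution and zero-event rule.

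Cost: SAP wording and a short simulation at the observed centre sizes, with no new data or patients. On the risk-difference scale, covariate adjustment would need standardisation.
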